6.4.4 Description of Pharmacodynamic Variables

Pharmacodynamic endpoints are as follows:

- Changes in immune parameters, e.g., lymphocyte subpopulations and plasma cytokines or chemokines in peripheral blood or in tumor

Pharmacodynamic analysis may be summarized in a separate report and is outside the scope of this SAP.

6.5 Data Quality Assurance

Report summaries will be generated using validated Base SAS® software, version 9.4 or higher, on a PC or server-based platform. Additional validated software may be used to generate analyses, as needed.

All SAS programs that create outputs or supporting analysis datasets will be validated by a second statistical programmer or biostatistician. At a minimum, validation of programs will consist of a review of the program log, review of output or dataset format and structure, and independent confirmatory programming to verify output results or dataset content. Additionally, all outputs will undergo a review by a senior level team member before finalization.

The content of the source data will be reviewed on an ongoing basis by project statistical programmers and statisticians. Data will be checked for missing values, invalid records, and extreme outliers through defensive programming applications, analysis-based edit checks, and other programmatic testing procedures. All findings will be forwarded to the project data manager for appropriate action and resolution.

7 STATISTICAL METHODS

7.1 General Methodology

Data will be analyzed by Precision for Medicine biostatistics personnel. Statistical analyses will be reported with tables, figures, and listings, presented in rich text format, and using recommended ICH numbering. Output specifications for all tables, figures, and listings will be in conformance with guidelines specified by the ICH in Appendix 7 of the *Electronic Common Technical Document Specification* (Apr 2003).

7.1.1 Reporting Conventions

Tables and figures will be summarized by treatment group. Tables summarizing demographics and other baseline characteristics will also include a column for all subjects combined. In general, all data collected and any derived data will be presented in subject data listings, for all screened subjects. Listings will be ordered by treatment

group, site, subject number, and assessment or event date. The treatment group presented in listings will be based on the planned assignment, unless otherwise noted.

In general, continuous variables will be summarized to indicate the study population sample size (N), number of subjects with available data (n), mean, SD, median, 25th (Q1) and 75th (Q3) quartiles, minimum, and maximum values. Categorical variables will be summarized by the population size (N), number of subjects with available data (n), number of subjects in each category, and the percentage of subjects in each category. Unless otherwise noted, the denominator to determine the percentage of subjects in each category will be based on the number of subjects with available data. Select ordinal data may be summarized using both descriptive statistics and counts and percentages of subjects in each category, as appropriate.

Non-zero percentages will be rounded to one decimal place. Rounding conventions for presentation of summary statistics will be based on the precision of the variable of summarization, as it is collected in its rawest form (i.e., on the eCRF or as provided within an external file) and are outlined as follows:

- The mean and median will be rounded to one more decimal place than the precision of the variable of summarization;
- Measures of variability (e.g., SD, SE) will be rounded to two more decimal places than the precision of the variable of summarization; and
- Minimum and maximum values will be presented using the same precision as the variable of summarization.

Other statistics (e.g., CIs) will be presented using the same general rules outlined above, or assessed for the most appropriate presentation based on the underlying data.

7.1.2 *Summarization by Visit*

Data summarized by study visit will be based on the nominal, scheduled visit label as reported on the eCRF.

Data collected at unscheduled visits will not be included in by-visit summaries, but will be considered when endpoint derivations potentially include multiple visits (e.g., determination of baseline value, determination of worst post-baseline value, etc.). All data will be included in subject listings.

7.1.3 *Data Handling Rules*

Unless otherwise noted, values reported as greater than or less than some quantifiable limit (e.g., “< 1.0”) will be summarized with the sign suppressed in summary tables and

figures, using the numeric value reported. Data will display on subject listings to include the sign.

7.1.4 *Standard Calculations*

Where appropriate, the calculated study day of each assessment or event will be presented with the assessment or event date on subject data listings, where study day will be determined as:

- The assessment/event date minus the date of first dose of study drug, if the assessment/event date is prior to the date of first dose; and
- The assessment/event date minus the date of first dose of study drug, plus one, if the assessment/event date is on or after the date of first dose.

Other variables requiring calculations will be derived using the following formulas:

- **Days:** A duration between two dates expressed in days will be calculated using the following conventions:
 - Later date – earlier date + 1, if the earlier date is on or after the date of first dose of study drug; or
 - Later date – earlier date, if the earlier date is prior to the date of first dose of study drug.
- **Months:** A duration expressed in months will be calculated by dividing the duration in days by (365.25 / 12);
- **Years:** A duration expressed in years will be calculated by dividing the duration in days by 365.25;
- **Change from Baseline:** Change from baseline will be calculated as the post-baseline value minus the baseline value;
- **Percentage Change from Baseline:** Percentage change from baseline will be calculated as the change from baseline divided by the baseline value, multiplied by 100.

7.2 *Analysis Populations*

The analysis populations are defined as follows:

- **Full Analysis Set:** All subjects enrolled in the study, also known as the “Intent-to-Treat” (ITT) population.

- **Safety Analysis Set:** All subjects who receive at least one dose of the investigational product, FLX475 (even a partial dose).

7.3 Study Subjects

7.3.1 *Disposition of Subjects*

Subject disposition will be summarized for all enrolled subjects by treatment group. Summaries will include the number and percentage of subjects in each analysis population, completing the treatment, discontinuing from treatment (by reason), completing the study, and discontinued from study (by reason).

7.3.2 *Protocol Deviations*

Protocol deviations (PDs) will be identified, logged, and reviewed during the course of the study. A determination of major versus minor PDs will be made according to the criteria outlined in the study protocol deviation review plan. A listing of all PDs will be provided. For purposes of CSR reporting, all important/major protocol deviations will be identified based on the following minimum criteria:

- Subjects who entered the study even though they did not satisfy the entry criteria.
- Subjects who developed withdrawal criteria during the study but were not withdrawn.
- Subjects who received the wrong treatment or incorrect dose.
- Subjects who received an excluded concomitant treatment.

7.3.3 *Demographic and Other Baseline Characteristics*

Demographic and baseline characteristics will be summarized descriptively for the Safety Analysis Set by treatment group. Gender, race, ethnicity, and baseline Eastern Cooperative Oncology Group (ECOG) performance status (PS) will be summarized with number and percentage presented for each category. Age, height, weight, and body mass index (BMI) at baseline will be described with summary statistics (n, mean, Std Dev, median, Q1, Q3, minimum, and maximum). BMI will be calculated as: weight (kg) / [height (cm) / 100]². In addition, primary cancer history will be summarized descriptively.

All demographic and baseline characteristics will be presented in a data listing.

7.4 Efficacy Evaluation

7.4.1 Primary and Secondary Efficacy Endpoints

Primary and secondary efficacy analyses will not be summarized due to early discontinuation of the study and a limited amount of available efficacy data.

7.4.2 Pharmacokinetic Analysis

Pharmacokinetic analysis may be summarized in a separate report and is outside the scope of this SAP.

7.4.3 Pharmacodynamic Analysis

Pharmacodynamic analysis may be summarized in a separate report and is outside the scope of this SAP.

7.5 Safety Evaluation

Safety analysis will be carried out for the Safety Analysis Set, to include all subjects who receive at least one dose of study drug. Subjects who do not complete the study, for whatever reason, will have all available data up until the time of termination included in the analysis. For safety analysis presented by study visit, the baseline value will be defined as the last value reported prior to the first FLX475 dose.

7.5.1 Extent of Exposure

Extent of exposure to study treatment FLX475 will be summarized for by treatment group for the Safety Analysis Set. The duration of exposure will be presented in days and calculated as the date of last dose of study drug minus the date of first dose of study drug, plus one. The total dose received will be determined using the drug dosing log CRF. For ipilimumab, number of infusions will be presented. A by-subject listing of FLX475 and ipilimumab administration data will be presented.

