- For subjects with average Grade 2 or 3 QTcF prolongation at doses of 75 mg or greater (measured at times other than during the up to 6-hour period immediately following an FLX475 dose when a threshold of Grade 3 QTcF prolongation should be used), interrupt treatment with FLX475 until resolution to Grade 0 or 1 or to the pretreatment severity grade, then resume treatment at 50 mg. Subjects with average Grade 2 or 3 QTcF prolongation while at the 50 mg or lower dose level of FLX475 (measured at times other than during the up to 6-hour period immediately following an FLX475 dose when a threshold of Grade 3 QTcF prolongation should be used) should be permanently discontinued from FLX475 treatment (unless it is determined by the investigator, in consultation with the Sponsor's medical monitor, to be in the subject's best interest to continue treatment either at 50 mg or at a reduced dose of 25 mg). Any subjects with observed QTcF prolongation of potential significance should have the ECG repeated for confirmation and electrolytes assessed and replaced as needed prior to action with study drug being taken. Any subjects with observed Grade 4 QTcF prolongation (including symptomatic/serious arrhythmia) should be treated appropriately and permanently discontinued from FLX475 treatment (unless it is later determined by the investigator, in consultation with the Sponsor's medical monitor, to be in the subject's best interest to continue treatment).
- The investigator may interrupt treatment with FLX475 for any other AE considered unacceptable for the individual subject, and treatment may be resumed at the previous lower dose level when resolved to Grade 0 or 1 or to pretreatment severity grade.
- If no lower dose level exists to which the subject may de-escalate, FLX475 should be discontinued.

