Other dose modifications may be acceptable but should be implemented at the investigator's discretion in consultation with the Sponsor's medical monitor, considering the subject's condition and the clinical benefit to the subject of continuing treatment at the current dose. If the subject requires a dose modification for an AE, then FLX475 administration should be interrupted, as necessary (and upon consultation with the Sponsor's medical monitor), until the AE resolves or stabilizes to an acceptable degree (generally to CTCAE Grade 0 or 1 or to pretreatment severity grade). Thereafter, treatment with FLX475 may be reinstated at the previous lower dose level. Subsequent reductions to successively lower dose levels can be made, if needed, as shown in [Table 2](#). More frequent laboratory monitoring may be required. Once the dose of study treatment has been reduced, it may not be increased at a later date without approval from the Sponsor's medical monitor. (Note that AEs known to be associated with ipilimumab may not require interruption or modification of FLX475 dosing.)

Table 2 Dose Modification Guidelines for FLX475-Related Toxicity

Treatment-Related Toxicity ^{a,b}	Management	Dose Adjustment
Grade 1 or Tolerable Grade 2		
	Continue treatment	No change
Intolerable Grade 2^c or Grade 3^{d, e}		
First occurrence	Interrupt FLX475 until resolved to Grade 0–1 or tolerable Grade 2 (or baseline)	Reduce FLX475 dose by 1 level (or if no lower dose level exists, discontinue drug)
Second occurrence (same toxicity or new toxicity)	Interrupt FLX475	Discuss with Sponsor
Grade 4^f: Discontinue Study Treatment		

Note: For grading see CTCAE version 5.0 ([Appendix 1](#)). Collect all CTC grades of adverse events, decreasing and increasing grade.

BMI = body mass index, CTCAE = Common Terminology Criteria for Adverse Events.

- a An interruption of study treatment for more than 21 days will require Sponsor's approval before treatment can be resumed.
- b Initiate optimal medical management for nausea, vomiting, hypothyroidism and/or diarrhea prior to any study treatment interruption or dose reduction.
- c Applicable only to Grade 2 toxicities judged by the subject or physician to be intolerable.
- d For Grade 3 toxicity, investigator will decide the probability of the event being related to 1 or both drugs and as to whether dose modification of either or both drugs is required.

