12.1.8.1 Extent of Exposure

The number of cycles/days on treatment, quantity of study treatments administered, and the number of subjects requiring dose reductions, treatment interruption, and treatment discontinuation due to AEs will be summarized. A by-subject listing of FLX475 administration data will be presented.

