6.3 Treatments

6.3.1 *Treatments Administered*

Subjects will take FLX475 orally once daily (QD) starting on Day 1 of Cycle 1. See [Section 6.3.1.1.1](#) for details of the planned dose administration schema.

Subjects will also receive ipilimumab. Ipilimumab 3 mg/kg will be administered IV Q3W for up to four doses.

The treatments to be used in this study are outlined in [Table 2](#).

Table 2 Study Treatments

Study Treatment	Formulation	Dose Levels	Route of Administration	Sourcing
FLX475	Tablets	100 mg (with possible dose reduction to 75, 50, or 25 mg) QD	Oral	Provided centrally by the Sponsor
Ipilimumab	Solution for infusion	3 mg/kg Q3W	IV infusion	Provided by the site

IV = intravenous, Q3W = once every 3 weeks, QD = once daily.

6.3.1.1 *FLX475 Administration*

All subjects will take FLX475 orally once daily on a continual basis. On days when ipilimumab is also administered (i.e., Day 1 of Cycles 1–4), FLX475 should be taken approximately 1 hour before the ipilimumab infusion.

The dose administration schema for FLX475 is provided below, along with instructions for dose modification.

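### SAP 7.5.1 reports FLX475 exposure as a first-to-last-dose span; no planned summary shows days actually dosed or dose relative to plan, and the protocol's counts of reductions and interruptions are missing

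*SAP*

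**What the plan says.** SAP 7.5.1 plans four things on exposure, for the Safety Analysis Set:

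- FLX475 duration in days, "calculated as the date of last dose of study drug minus the date of first dose of study drug, plus one". No days are deducted.
- Total FLX475 dose: "The total dose received will be determined using the drug dosing log CRF". The section does not say how this will be summarized.
- The number of ipilimumab infusions.
- A listing: "A by-subject listing of FLX475 and ipilimumab administration data will be presented".

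Protocol 12.1.8.1 asks for more. Its sentence opens "The number of cycles/days on treatment, quantity of study treatments administered" and goes on to counts of subjects who needed dose reduction, interruption or discontinuation because of adverse events.

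Interruptions with restart are part of the regimen. The planned dose is "100 mg (with possible dose reduction to 75, 50, or 25 mg) QD" (SAP 6.3.1, Table 2). For Grade 2 or 3 QTcF prolongation at 75 mg or above, Protocol 10.5.1 says to "interrupt treatment with FLX475 until resolution to Grade 0 or 1 or to the pretreatment severity grade, then resume treatment at 50 mg". Protocol Table 2 orders an interruption, then a one-level reduction, at the first intolerable Grade 2 or Grade 3 related toxicity. Its footnote a reads "An interruption of study treatment for more than 21 days will require" Sponsor approval before restarting, so shorter holds need none and longer ones are possible.

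**The concern.** A subject who stops FLX475 for toxicity and later restarts has the gap reported as exposure. Cycle counts would not reveal it either, because Protocol 8.2.2 keeps cycle numbers running through interruptions.

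Safety and tolerability is a primary objective. The SAP drops the efficacy summaries (7.4.1, 7.7) and places pharmacokinetics outside its scope (7.4.2), so the exposure and safety tables carry the report. A reader of those tables will want to know how much of the daily regimen subjects could sustain alongside ipilimumab. A span and a total in milligrams, each summarized over the group, do not answer that subject by subject.

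The counts of reductions and interruptions would at least have signalled the gaps. They appear in neither SAP 7.5.1 nor SAP 7.5.2, where the overview and the tables by system organ class cover discontinuations only. SAP section 4 says that changes from the protocol's methods will be explained in the SAP, and SAP 7.7 lists only the efficacy change.

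**Working it through.** The documents give no exposure or dose-intensity figure to reproduce, and no interruption frequency or length. The dosing courses below are therefore assumptions, built from the protocol's 100 mg dose, its reduction levels and the 21-day threshold.

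Formulas:

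- SAP duration = last dose date − first dose date + 1
- Days dosed = SAP duration − days off drug
- Overstatement = SAP duration / days dosed − 1
- Relative dose intensity (RDI) = total mg / (100 mg × SAP duration)

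Courses over a 126-day span (6 cycles × 21 days; planned dose 126 × 100 = 12,600 mg):

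| Course | SAP duration | Days dosed | Overstatement | Total mg | RDI |
|---|---|---|---|---|---|
| 126 d at 100 mg | 126 | 126 | 0% | 12,600 | 100% |
| 42 d at 100, 7 off, 77 at 50 | 126 | 119 | 126/119 − 1 = 5.9% | 4,200 + 3,850 = 8,050 | 63.9% |
| 42 d at 100, 21 off, 63 at 50 | 126 | 105 | 126/105 − 1 = 20% | 4,200 + 3,150 = 7,350 | 58.3% |
| 42 d at 100, 21 off, 63 at 75 | 126 | 105 | 20% | 4,200 + 4,725 = 8,925 | 70.8% |
| 42 d at 100, 21 off, 63 at 100 | 126 | 105 | 20% | 4,200 + 6,300 = 10,500 | 83.3% |

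The overstatement depends on the length of the hold relative to the span. A 21-day hold in a 63-day span gives 63/42 − 1 = 50%. The same hold in a full 35-cycle course (735 days) gives 735/714 − 1 = 2.9%.

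The RDI shortfall has two sources. In the third row, 12,600 − 7,350 = 5,250 mg is missing: 21 × 100 = 2,100 mg from the hold and 63 × 50 = 3,150 mg from the reduction. Only the first part concerns the duration formula. That is why days dosed and RDI are both useful.

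Total dose alone does not identify the course. In an 84-day span, 28 days at 100 mg, 14 off and 42 at 50 mg gives 2,800 + 2,100 = 4,900 mg, the same total as 49 days at 100 mg. Read with duration (84 against 49 days) the two courses are distinct, but that pairing is available per subject only in the listing.

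**The case against.** The strongest reply is that last minus first plus one is an ordinary definition of treatment duration and nothing is wrong with it. The protocol does not define days on treatment as days dosed, and its continuous cycle counting fits a calendar span. Total dose and a by-subject listing are in the same paragraph, so in a study planned for about 20 subjects and stopped early, anyone can work out intensity. All of this stands. What it leaves open is that the SAP specifies no summary of days dosed or intensity, and that the protocol's counts were dropped without being declared.

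A reader might infer four stronger things that the documents do not support:

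- **That nothing shows how much of the 100 mg regimen was received.** Total dose from the dosing log is planned, and administration is listed by subject.
- **That subjects who could not stay on drug look fully exposed.** This could be said only of the duration figure. In the third row of the table, 7,350 mg over 126 days is plainly short of 12,600 mg.
- **That exposure is overstated most where toxicity was worst.** Protocol 10.5.1 generally directs permanent discontinuation for clinically significant organ-related Grade 4 events, Grade 4 QTcF prolongation and Grade 4 toxicity in Table 2, with exceptions. A subject who stops for good adds no gap after the last dose. The inflation needs a restart, so it falls mainly on toxicity that resolved.
- **That the run-in decision is affected.** The run-in is judged on dose-limiting toxicities in Days 1–21, when FLX475 modification is generally not permitted (Protocol 10.4, 10.5.1).

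**Conclusion.** The point holds as a gap in the planned summaries, not as an error in the formula. Three facts rest on the text alone: the reported span includes off-drug days before a restart, no summary gives days dosed or dose relative to plan, and the promised counts of reductions and interruptions are missing without being declared.

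The size is illustrative: +5.9% for a 7-day hold and +20% for a 21-day hold in 126 days, ranging from +2.9% to +50% as the span around a 21-day hold changes from 735 to 63 days. The actual effect depends on how many subjects were held and restarted, which the documents do not say; with no such subjects it is zero.

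The consequence is small. The analysis is descriptive, and no test, sample size or decision rule uses this variable. It is a cheap improvement to the reporting of a primary objective.

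**What to change.** In SAP 7.5.1:

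1. Keep the present formula and label the result 'treatment duration'.
2. Add days on FLX475 = treatment duration − days not dosed, from the dosing log.
3. Add relative dose intensity = total mg received / (starting assigned daily dose × treatment duration). Fix the denominator at the starting dose so that later reductions show.
4. Restore the counts of subjects with FLX475 interruptions and reductions due to adverse events from Protocol 12.1.8.1, or declare and explain their omission in SAP 7.7.

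Reporting the number of subjects below 80% intensity is optional. Protocol 9.1.3 uses 80% only to decide replacement in Cycle 1 of the run-in, so a whole-course cut-off would be a new choice.

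The cost is two derived variables and the restored counts. No new data are needed if the dosing log CRF records dates and dose levels, which its planned use for total dose suggests but the SAP does not spell out. The downside is slightly more programming and slightly less favourable exposure figures.

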7.5.2 Adverse Events

All subjects will be assessed regularly for the potential occurrence of adverse events (AEs) from the date of informed consent to 90 days after the last dose of study treatment. The incidence of treatment-emergent adverse events (TEAEs) will be summarized and tabulated using Medical Dictionary for Regulatory Activities (MedDRA), by System Organ Class (SOC) and Preferred Term (PT). A TEAE is defined as an AE that first occurs or worsens in severity on or after the first dose of FLX475. All adverse events recorded in the eCRF will be presented in data listings.

The National Cancer Institute (NCI)/CTCAE v5.0 will be used to grade both clinical and laboratory AEs. A subject with several occurrences of the same AE will be counted once

and classified by the most severe occurrence. AEs with missing severity ratings will be classified as having unknown severity, but will be assigned Grade 3 severity for analysis and summarization.

The relationship of each AE to the study treatment will be classified as related or unrelated; an AE that is possibly, probably or definitely related to study treatment will be considered related. Any AE with an eCRF description of related will be considered related. A subject with several occurrences of the same AE will be counted once and classified as related if at least one of them is classified as related. An AE with a missing relationship to study treatment will be assumed to be related to study treatment for the purpose of analysis and summarization. Relationship of AEs to FLX475 and ipilimumab will be separately recorded and analyzed.

An overview of adverse events for the Safety Analysis Set will be provided, summarizing the incidence of the following:

- Any DLT;
- Any TEAEs; FLX475-related TEAEs; ipilimumab-related TEAEs;
- Any NCI/CTCAE Grade ≥ 3 TEAEs; FLX475-related NCI/CTCAE Grade ≥ 3 TEAEs; ipilimumab-related NCI/CTCAE Grade ≥ 3 TEAEs;
- Any serious TEAEs; FLX475-related serious TEAEs; ipilimumab-related serious TEAEs;
- Any discontinuation of study treatment due to TEAEs; discontinuation of FLX475 due to FLX475-related TEAEs; discontinuation of ipilimumab due to ipilimumab-related TEAEs;
- Any NCI/CTCAE Grade 5 TEAEs; FLX475-related NCI/CTCAE Grade 5 TEAEs; ipilimumab-related NCI/CTCAE Grade 5 TEAEs.

TEAE summaries by SOC and PT will be provided for the following:

- TEAEs (overall and FLX475 or ipilimumab related);
- Grade ≥ 3 TEAEs (overall and FLX475 or ipilimumab related);
- TEAEs leading to discontinuation of study treatment (overall and FLX475 or ipilimumab related);
- Serious TEAEs (overall and any serious FLX475 or ipilimumab related);

In addition, a summary will be provided for the number and percentage of subjects with TEAEs by the highest NCI CTCAE grade. For this summary, subjects with multiple adverse events will be counted only once by the highest NCI CTCAE grade within an SOC and preferred term.

7.5.3 *Deaths, Other Serious Adverse Events, and Other Significant Adverse Events*

All deaths during the study, including the post treatment follow-up period, will be listed by subject, to include the primary cause of death. Serious AEs, AEs of clinical interest, and AEs associated with DLT will be provided in separate subject data listings.

7.5.4 *Clinical Laboratory Evaluation*

Hematology and chemistry parameters will be summarized by visit for the Safety Analysis Set. Only scheduled visit values will be included in this summary.

All clinical laboratory data will be listed by subject. Values outside the normal ranges will be flagged and toxicity grades will be displayed for relevant parameters. Hematology and chemistry measurements identified as abnormal (i.e., outside the normal range) will also be listed separately by subject, laboratory test, and unit.

7.5.5 *Vital Signs, Physical Findings, and Other Observations Related to Safety*

7.5.5.1 *Vital Signs*

Vital signs measurements include heart rate, respiratory rate, temperature, systolic blood pressure, and diastolic blood pressure. Vital signs will be listed by subject.

7.5.5.2 *12-Lead Electrocardiogram*

ECG measurements include heart rate, PR interval, RR interval, QRS interval, QT interval, QTc intervals. The number and percentage of subjects with elevated QTcF values (≥ 450 msec, > 480 msec, and > 500 msec) at baseline and any time post baseline will be presented. In addition, the number and percentage of subjects with QTcF values that increase by > 30 msec and > 60 msec from baseline to any time post baseline will be presented. ECG data will also be listed by subject.

7.5.5.3 *Physical Examination*

Results of the physical examination will be presented in subject data listings.

7.5.5.4 *Prior and Concomitant Medications*

Prior and concomitant medications will be coded using the World Health Organization Drug Dictionary (WHODD). Prior medications include medications that were stopped

before the first dose of FLX475. Concomitant medications include medications that (1) started before the first dose of FLX475 and are continuing at the time of the first dose of FLX475, or (2) started on or after the date of the first dose of FLX475 up to 30 days after the subject's final dose. All medications will be presented in subject data listings.

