APPENDIX 1 COMMON TERMINOLOGY CRITERIA FOR ADVERSE EVENTS (CTCAE) VERSION 5.0

The Common Terminology Criteria for Adverse Events (CTCAE v5.0, published 27 November 2017) provides descriptive terminology to be used for adverse event reporting in the clinical trials. A brief definition is provided to clarify the meaning of each AE term. To increase the accuracy of AE reporting, all adverse event terms in CTCAE v5.0 have been correlated with single-concept MedDRA terms.

The Common Terminology Criteria for Adverse Events v5.0 grading refers to the severity of the AE. The Common Terminology Criteria for Adverse Events grades 1 through 5, with unique clinical descriptions of severity for each AE, are based on this general guideline:

Grade	CTCAE Status
1	Mild: asymptomatic or mild symptoms; clinical or diagnostic observations only; intervention not indicated
2	Moderate: minimal, local, or noninvasive intervention indicated; limiting age-appropriate instrumental activities of daily living (ADL) ^a
3	Severe or medically significant but not immediately life-threatening: hospitalization or prolongation of hospitalization indicated; disabling, limiting self-care ADL ^b
4	Life-threatening consequences: urgent intervention indicated
5	Death related to adverse event

ADL = activities of daily living, CTCAE = Common Terminology Criteria for Adverse Events.

^a Instrumental ADL refers to preparing meals, shopping for groceries or clothes, using the telephone, managing money, etc.

^b Self-care ADL refers to bathing, dressing and undressing, feeding self, using the toilet, taking medications, and not bedridden.

Adapted from the Cancer Therapy Evaluation Program, NCI. CTCAE v5.0

For further details regarding MedDRA, refer to the MedDRA website at:
<http://www.meddra.org>

**APPENDIX 2 EASTERN COOPERATIVE ONCOLOGY GROUP
PERFORMANCE STATUS SCALE**

ECOG Performance Status Scale* Definitions Rating Criteria	
Score (Grade)	Status
0	Fully active, able to carry on all pre-disease performance without restriction
1	Restricted in physically strenuous activity but ambulatory and able to carry out work of a light or sedentary nature, e.g., light house work, office work
2	Ambulatory and capable of all self-care but unable to carry out any work activities. Up and about more than 50% of waking hours
3	Capable of only limited self-care, confined to bed or chair more than 50% of waking hours
4	Completely disabled. Cannot carry on any self-care. Totally confined to bed or chair
5	Dead

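### SAP 7.5.2 grades every AE with missing severity as Grade 3, with no exception for a fatal AE, which would then be left out of the Grade 5 rows

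*SAP*

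**What the plan says.** SAP 7.5.2 sets the rule for an AE without a grade: "AEs with missing severity ratings will be classified as having unknown severity, but will be assigned Grade 3 severity for analysis and summarization". It does not distinguish fatal, serious or other events. The protocol's AE analysis section (12.1.8.2) has a rule for missing causality but none for missing severity, so this SAP sentence alone governs.

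The same SAP section then builds several outputs on the grade. The overview table has rows for "Any NCI/CTCAE Grade 5 TEAEs; FLX475-related NCI/CTCAE Grade 5 TEAEs; ipilimumab-related NCI/CTCAE Grade 5 TEAEs" and a row for "Any NCI/CTCAE Grade ≥ 3 TEAEs". The highest-grade summary states that "subjects with multiple adverse events will be counted only once by the highest NCI CTCAE grade within an SOC and preferred term". Other overview rows are selected by seriousness: "Any serious TEAEs; FLX475-related serious TEAEs; ipilimumab-related serious TEAEs".

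Protocol Appendix 1 gives the general CTCAE scale and defines Grade 5 as "Death related to adverse event". Separately, SAP 7.5.3 provides that "All deaths during the study, including the post treatment follow-up period, will be listed by subject", with the primary cause.

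**The concern.** A blank grade does not always mean that severity is unknown. If the AE is recorded as having ended in death, its CTCAE grade follows from that outcome. The SAP rule ignores the outcome and substitutes a lower grade.

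The rule also differs from the one beside it. In SAP 7.5.2 a missing relationship to treatment takes the least favourable value (related), whereas missing severity takes a middle grade even when the outcome shows a higher one.

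SAP 7.4.1 and 7.7 drop the efficacy summaries because the study stopped early. Of the two primary objectives in SAP 5.1, only safety and tolerability is still analysed under this plan. The Grade 5 rows are the most serious lines of the AE overview, and in a study this small a single subject is visible in them.

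**Working it through.** The plan has no figure to reproduce here, so the check is a trace. Take one hypothetical TEAE with a fatal outcome and a blank grade, apply the SAP rule, and follow it through each output. Do the same with grade taken from the outcome, as Appendix 1 implies.

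| Output (SAP section) | Selected by | Rule as written | Grade from fatal outcome |
|---|---|---|---|
| Grade 5 rows (7.5.2) | grade | 0 subjects | 1 subject in the any row, and in each related row that applies |
| Highest-grade summary (7.5.2) | grade | Grade 3, unless the subject has a higher-graded occurrence of the same term | Grade 5 |
| Grade ≥ 3 row (7.5.2) | grade | 1 subject | 1 subject |
| Serious TEAE row (7.5.2) | seriousness | 1 subject | 1 subject |
| SAE listing (7.5.3) | seriousness | listed | listed |
| Death listing (7.5.3) | death | listed | listed |

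Only the first two lines change. No passage in either document sets the grade from a fatal outcome or reconciles the Grade 5 rows with the death listing, so nothing later in the plan would correct them.

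Scale of one affected subject, as an illustration:

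- Planned size of 20 (SAP 7.6): 0/20 = 0% as written against 1/20 = 5.0%.
- Safety run-in of 6 (SAP 7.6), if no one else were treated: 0/6 = 0% against 1/6 = 16.7%.

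The number actually treated before the early stop is not in the documents. These percentages show what one subject weighs; they do not estimate how often the case occurs.

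Next, take an ungraded event that was life-threatening but not fatal. The general scale in Appendix 1 points to Grade 4, and the rule gives Grade 3. The overview has no Grade 4 row, so the only change is in the highest-grade summary (3 instead of 4). The Grade ≥ 3 and serious rows count the subject either way. The event belongs in neither the Grade 5 rows nor the death listing.

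Last, take an ungraded event that was truly Grade 1 or 2. The rule raises it to Grade 3 and adds it to the Grade ≥ 3 row. For non-fatal events the default can therefore err in either direction.

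**The case against.** The strongest reply is that the case will hardly ever arise. Protocol 11.5.1 and SAP 6.4.2.1 require a CTCAE grade for every AE. Protocol 11.7.1 requires SAE reports within 24 hours, followed by detailed documents including autopsy reports. SAP 6.5 has the data checked for missing values, with findings sent to the data manager for resolution. A fatal AE with no grade at lock would have to pass all of these, and neither document reports a missing grade. This stands, and it keeps the point minor.

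It is also true that no event is lost. The fatal TEAE remains in the Grade ≥ 3 and serious rows, the SAE and death listings, and the full AE listing. The error is confined to the Grade 5 rows and the highest-grade summary.

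Three stronger readings are tempting, and the documents do not support them:

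- A reader might infer that a life-threatening event also goes missing from the Grade 5 rows. A non-fatal event was never due to appear there.
- A reader might infer that the rule biases the AE tables downward in general. It does so only for events that are truly Grade 4 or 5; it inflates those that are truly Grade 1 or 2.
- A reader might take any excess of the death listing over the Grade 5 count as proof of the error. That listing covers all deaths, including those in follow-up, while progression of the cancer is not an AE (Protocol 11.5.1, SAP 6.4.2.1). It can exceed the Grade 5 count by design, so only AE-related deaths are comparable.

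None of this answers the narrow point: when the rule does meet a fatal AE, it gives the wrong grade.

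**Conclusion.** The point holds for fatal AEs with a missing grade, and as a minor one. As written, the rule would place such an event at Grade 3, leave it out of the Grade 5 rows, and under-grade it in the highest-grade summary. Whether this changes any reported number depends on a fatal TEAE reaching lock ungraded, which the plan's own controls make unlikely. If it happened once, the Grade 5 row would be short by one subject, with the weight shown in the working.

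The conclusion assumes that the programmers apply the sentence literally and that the outcome of the AE itself is recorded as death. A subject who dies of progression while an unrelated AE is ongoing is not affected. For non-fatal events the documents give no firm ground for calling the Grade 3 default wrong in a particular direction.

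**What to change.** Amend the missing-severity sentence in SAP 7.5.2 to say:

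1. Missing grades on serious AEs are queried before database lock.
2. If the grade is still missing, the AE is assigned Grade 5 when that AE's own outcome is death, and Grade 3 otherwise.
3. The tables carry a footnote with the number of imputed grades.

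An optional addition is Grade 4 when the life-threatening seriousness criterion is recorded for that AE. This is only approximate. Appendix 1 is a general guideline with event-specific descriptions, and footnote f to Protocol Table 2 recognises Grade 4 laboratory abnormalities that are not life-threatening. The fatal-outcome clause is the part that the documents firmly support.

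The cost is one sentence and a few lines of derivation code. The derivation relies on AE outcome or seriousness fields. The eCRF is not among the documents and their capture is inferred from the SAE definition (Protocol 11.5.2, SAP 6.4.2.2), so the fields should be confirmed before the wording is fixed.
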